9.2 REPORTING PROCEDURES

> REPORTING OF ADVERSE EVENTS TO FDA

- Written IDE Safety Reports
- Telephoned IDE Safety Reports Fatal or life-threatening suspected adverse reactions

> Reporting Adverse Events to Other External Entities

 Adverse event reports will also be submitted to the MED-EL Corporation, which has provided a Right of Reference Letter for the MAESTRO Cochlear Implant system in accordance with their respective reporting guidelines.

> Reporting Adverse Events to the Human Studies Committee

- The Principal Investigator will reports to the HSC any serious adverse events that are unexpected and related/possibly related to research within 7 calendar days from the time the PI became aware of the event.
- Any unexpected and study-related death will be reported to the HSC within 24 hours of PI's knowledge of the event by email or telephone.
- The PI will report to the HSC all non-serious adverse events that are unexpected and related or possibly related to the research within 30 calendar days from the time the PI became aware of the event.

• The PI will promptly report to the HSC Unanticipated Problems (UAPs) involving risks to the subjects or others.

9.3 Withdrawal of Subjects due to Adverse Events

1. Reporting of Unexpected and Related/Possibly Related Events Serious Adverse Event (SAE)

Any serious adverse event will be reported to the HSC. These SAE include those that both (i) are unexpected and related/possibly related to research; and (ii) occur while the subject is enrolled in the study or that occur within 30 days of the conclusion of the subject's participation in the study, of which the PI or study staff become aware. In order to determine whether a specific adverse event is unexpected, the PI will consider whether the event is consistent with the risks described in the protocol-related documents (e.g. protocol, consent form, Investigator's Brochure). In order to determine whether a specific adverse event is related or possibly related to subject's participation in the research, the PI will consider the temporal relationship between the event and the investigational product being studied or study procedure. If an adverse event is at least partially caused by the procedures and /or investigational products, it will be considered related/possibly related to research.

Any adverse events that are serious, unexpected and related or possibly related to the study will be reported to the HSC within 7 calendar days from the time the PI becomes aware of the event. Any unexpected and study-related death will be reported to HSC within 24 hours of the PI's knowledge of the event by e-mail or telephone. A completed AE report form will be submitted to HSC within 7 calendar days of initial HSC notification. If the PI becomes aware more than 30 days after the conclusion of a subject's participation of a serious adverse event that is both related to the research and unexpected, the PI will report the event to HSC at the time he/she becomes aware of it.

Non-Serious Adverse Event

All non-serious adverse events that are unexpected and related or possibly related to the research will be reported to the HSC within 30 calendar days from the time the PI becomes aware of the event.

- 2. Reporting of Expected and Related/Possibly Related Events The PI will submit a summary report to the HSC for all serious and non-serious events that are expected and related/possibly related to the study at the time of continuing review.
- 3. **Reporting of Unanticipated Problems** The PI will promptly report to the HSC Unanticipated Problems (UAPs) involving risks to subjects or others. In order to determine whether a specific problem constitutes a UAP, the PI will consider the following:
 - The vast majority of adverse events occurring in human subjects do not represent UAP because most AEs are expected in the context of known toxicities or side effects of the research procedures and/or are due to the natural history of subjects' underlying diseases and conditions;
 - a small proportion of AEs do represent UAPs; and
 - UAPs may include events that are not adverse events.

All UAPs involving risks to subjects or others will be reported in writing to the HSC within 7 calendar days from the time the PI becomes aware of the event. If a UAP or an unexpected SAE results in a subject's death or was potentially life-threatening, the PI will notify HSC through e-mail or phone within 24 hours from the time the event is identified. A follow-up report will be submitted at a later date when more information is available. The PI will notify HSC through e-mail or phone within 24 hours from the time the event is identified for UAPs that take the form of a data loss.

9.3 Withdrawal of Subjects due to Adverse Events

• Subjects experiencing major adverse events will be referred for appropriate care as needed. The severity of adverse events will be determined by the investigator in

consultation with the HSC. Briefly, events that lead to irreversible or permanent disability of the patient will be considered serious and the subject will be reminded that participation in the study is voluntary and that withdrawal is possible at any time. If the subject remains interested in continuing to participate in the study, then after receiving the appropriate care, data will continue to be collected from the subject at follow-up visits as described in the study design. Medical attention and follow-up for any adverse events will continue until the adverse health concern has resolved or if not, then continued indefinitely. If a subject withdraws from the study due to an adverse event, he/she will be replaced by recruiting a new study participant from clinic. The reasons for withdrawal or termination will of course be reported and documented at the time of the occurrence. In principle, then, more than 10 subjects may end up with an implant based on their participation in the study.

10. STATISTICAL METHODS/DATA ANALYSIS

10.1 Primary endpoint(s) or outcome measure(s)

The study has a primary endpoint of one year following cochlear implant surgery for ten study participants. Outcomes measures include audiologic measures and subjective questionnaires as described in previous sections, as well as safety assessments completed throughout the study.

Our previous work has established the importance of these physiological, psychophysical, audiologic tests, questionnaires on efficacy, and safety measures as a comprehensive method for assessing the outcomes of cochlear implant surgery. In particular, the use of these measures will allow us to obtain both objective and subjective data to assess the safety and efficacy of cochlear implant placement in patients with single sided deafness and thereby understand how cochlear implant placement has influenced patients' hearing and quality of life. By comparing our findings and measures to data obtained in other patient populations (such as patients with single sided deafness who do not undergo cochlear implantation), we will better understand whether cochlear implant placement in this patient population has improved safety and efficacy compared to no treatment.

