3.2 Allocation to Treatment

Because our study is a repeated-measure, single subject experimental design with up to ten replications, there is no proposed plan or procedure for allocating study participants to various cohorts of arms of the proposed clinical investigation.

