4. SUBJECT SELECTION

4.1 Subject Inclusion Criteria

- 18 years of age or older with the ability to provide informed consent
- English as the primary language
- Medically and psychologically suitable
- Willing to receive/have received meningitis vaccinations
- Unsuccessful trial of non-invasive hearing amplification devices or tinnitus treatment as defined by standard of care of six months
- Able to pay for all care received through the study, either through the subject's insurance company or through self-pay
- Able to comply with study requirements, including travel to the investigational sites
- Severe to profound sensorineural hearing loss (\geq 70 dB thresholds between 500 and 4000 Hz) in the worse ear with \leq 20% CNC word scores
- Duration of single-sided deafness \geq one year
- Tinnitus localized to the affected ear, both ears or in the head localized to the affected ear, both ears, or in the head
 - Expected subjects include those with:
 - Unilateral hearing loss secondary to viral or bacterial infection, such as meningitis or labyrinthitis
 - Ménière's disease
 - Sudden sensorineural hearing loss
 - Vascular disease affecting the inner ear
 - A combination of any number of the above conditions

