5.2 Study Drug/Device Compliance/Adherence

Because the cochlear implant system is an implanted device, there are few concerns regarding compliance and adherence compared to most drug-based clinical trials. Our study is designed as a prospective, repeated-measure single subject trial. Participants in the experimental group will serve as their own controls. Throughout the study, we will confirm that subjects have been using the device through routine clinical follow-up and questionnaires at each appointment. Both qualitative and quantitative measures will be obtained to determine if subjects are benefiting from the cochlear implant system, and the individual activation parameters at each visit will be compared to the prior visit to ensure that settings on the device have not been altered or changed between visits.

Although we anticipate that the vast majority of subjects will derive a safe and substantial clinical benefit from use of the cochlear implant system, if a given subject is non-compliant or non-adherent with use of the cochlear implant system or external sound processor, then we will collect a final set of qualitative and quantitative measures and simply follow their outcomes through routine clinical exams. This approach will allow for monitoring of any

adverse safety or health concerns that may arise. Thus, no subjects in our study will be formally withdrawn for non-compliance or non-adherence and all study participants will be followed for one year after cochlear implant surgery. Any patient choosing to withdraw from the study will be replaced by a new study participant recruited from the clinic. The reasons for withdrawal or termination will of course be reported and documented at the time of occurrence.

If a subject withdraws or is terminated after implantation, a new subject will replace him or her. In principle, then, more than 10 subjects may end up with an implant based on their participation in the study.

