10.2 Secondary endpoints or outcome measure(s)

The secondary outcome measure of this study is the effect of cochlear implantation on tinnitus suppression in patients with tinnitus in the non-hearing ear. Outcomes will be assessed using the Tinnitus Handicap Inventory and auditory brainstem response testing as previously indicated. Prior studies have indicated that cochlear stimulation via a cochlear implant device can suppress tinnitus. By comparing our findings and measures to data obtained from patients with single sided deafness who do not undergo cochlear implantation, we will better understand the utility of cochlear implantation for tinnitus suppression in this patient population.

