10.3 Sample Size Determination

Our study will recruit ten participants for placement of a MAESTRO Cochlear Implant device with follow-up measurements and assessments for one year post-operatively. Although our study is limited to a small sample size of ten patients, the single subject research design will allow each subject to serve as his or her own control, accommodating heterogeneity of the subjects' backgrounds and providing adequate power to test the major hypotheses. Previous studies have used a similar study design and sample size, with statistically significant findings regarding efficacy and safety of cochlear implants in patients with single sided deafness. Given that single-sided deafness is an experimental indication for cochlear implantation, it is appropriate to assess efficacy in a small cohort prior to recruiting more subjects. This will allow us to avoid unnecessary surgery in patients who may not benefit from this intervention.

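### Section 10.1 looks to undefined, possibly treated, non-implanted patients for evidence of efficacy against no treatment (10.2 does similarly for tinnitus), a conclusion that contrast cannot support

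*Combined protocol and SAP*

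**What the plan says.** The design has one arm. Section 10.3 states: "Our study will recruit ten participants for placement of a MAESTRO Cochlear Implant device". Section 3.2 says that "there is no proposed plan or procedure for allocating study participants to various cohorts of arms", and section 5.2 that "Participants in the experimental group will serve as their own controls". Section 10.5, the effectiveness analysis, compares each subject before and after implantation and mentions no external data.

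Section 10.1 nevertheless ends by bringing in outside patients, namely those without an implant: "By comparing our findings and measures to data obtained in other patient populations (such as patients with single sided deafness who do not undergo cochlear" (the sentence is cut here). The aim is to understand better whether implantation "has improved safety and efficacy compared to no treatment". Section 10.2 does something similar for tinnitus: "By comparing our findings and measures to data obtained from patients with single sided deafness who do not undergo cochlear implantation", the investigators expect to understand the utility of implantation for tinnitus suppression.

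The trial's own subjects are closely selected. Section 4.1 requires an "Unsuccessful trial of non-invasive hearing amplification devices or tinnitus treatment as defined by standard of care of six months". It also requires ability to pay for care, ability to travel to the sites, and at least one year of deafness, and it lists tinnitus. Section 4.2 excludes deafness of ten years or more, major depression or anxiety, and unrealistic expectations.

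**The concern.** A comparison with people who did not receive the implant shows the effect of the implant only if the two groups would otherwise have had the same outcomes. Here one group has passed a long list of filters and the other is described only as not implanted. Several filters plausibly bear on the questionnaire outcomes (THI, SF-36, hearing handicap), and they need not act in the same direction. Failure of earlier treatment could select people with worse scores, while excluding major depression or anxiety could select people with better ones. The documents do not allow the net direction to be predicted.

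What is at stake is how the result is read. Section 10.1 is the primary endpoint section. A reader could take a non-randomised contrast with unspecified patients as controlled evidence of efficacy, when the design contains no untreated control group.

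**Working it through.** **1. The plan's own figure.** There is none to reproduce. Section 10.3 gives ten subjects and calls the power adequate, with no effect size, SD or numerical power. Sections 10.1 and 10.2 give no number of comparison patients and no expected difference.

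**2. What is required of each group.**

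| Feature | Trial subjects | Comparison patients (10.1, 10.2) |
|---|---|---|
| Failed six-month device or tinnitus treatment trial | Required (4.1) | Not stated |
| Deafness of one to under ten years | Required (4.1, 4.2) | Not stated |
| Able to pay and to travel | Required (4.1) | Not stated |
| No major depression or anxiety | Required (4.2) | Not stated |
| Tinnitus | Listed (4.1) | Not stated, even in 10.2 |
| Untreated | Not applicable | Not stated |
| Instruments and visit times | 3.1, 8.2, schedule of events | Not stated |
| Data source, matching or adjustment | Not applicable | Not stated |

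The only matching in the protocol (7.1) concerns the proportions of women and minorities enrolled, relative to past trials. It does not concern a comparison group.

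**3. Not implanted is not the same as untreated.** Sections 1.1 and 1.2 describe CROS hearing aids and bone-conduction devices as existing options in the United States. A non-implanted patient may be using one. The comparison could therefore be with a mixture of treated and untreated people, whatever the selection differences.

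**4. Tinnitus.** A comparison patient without tinnitus has little or no THI score to lose. Using change from baseline would therefore not make the groups in 10.2 comparable.

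**5. Illustration of size, on assumed inputs.** Let the implant effect be zero. Let the 10 trial subjects differ from *m* comparison patients by *d* SD on the quantity compared, through selection alone. For a two-sided 0.05 two-sample t-test:

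- degrees of freedom = 10 + *m* − 2
- noncentrality = *d* / √(1/10 + 1/*m*)
- chance of p ≤ 0.05 = both tails of the noncentral t beyond the critical value

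For *d* = 0.5 and *m* = 20: √(0.10 + 0.05) = 0.387, noncentrality 0.5/0.387 = 1.29, 28 df, critical value 2.048, result 23.9%.
For *d* = 0.5 and *m* = 50: √(0.10 + 0.02) = 0.346, noncentrality 0.5/0.346 = 1.44, 58 df, critical value 2.002, result 29.5%.

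| Assumed imbalance (SD) | *m* = 20 | *m* = 50 |
|---|---|---|
| 0.25 | 9.6% | 10.9% |
| 0.5 | 23.9% | 29.5% |
| 0.75 | 46.4% | 56.7% |
| 1.0 | 70.3% | 81.0% |

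Section 10.5 speaks of non-parametric tests. A Mann-Whitney simulation (10,000 runs, normal data) at 0.5 SD gives 16.5%, 27.2% and 29.8% for 10, 50 and 100 comparison patients. For a fixed imbalance, more comparison patients raise the rate: they sharpen the estimate of a biased quantity.

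**The case against.** The strongest reply is that this is a closing sentence of rationale and not an analysis. Section 10.1 hopes to understand better whether there was a benefit. The operative plan is 10.5, which is within subject. That stands, and it limits the point: no effectiveness analysis specified in 10.5 depends on outside data. It does not remove the point, because the stated target of the comparison is still efficacy against no treatment, and nothing in the plan makes that target reachable.

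Several stronger readings are tempting, and the documents do not support them:

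- *The plan promises a verdict.* It does not; the wording is softer.
- *Section 10.2 also claims efficacy against no treatment.* It speaks only of utility for tinnitus suppression.
- *The plan admits ineligible comparison patients.* It says nothing about their eligibility. The gap is an inference from silence.
- *Subjects are selected on willingness to have surgery.* This is not a listed criterion. Whether every subject must have tinnitus is also unclear: 4.1 lists it, but 2.2 and 7.2 read as if some subjects may lack it or have little.
- *The rates above are the trial's false-positive rate.* Neither 10.1 nor 10.2 specifies a test against outside patients, and a baseline imbalance of a given size need not carry over to change scores.
- *The before/after comparison is free of confounding.* It avoids differences between patients, but the study is unmasked (3.1), many outcomes are self-reported, and time, expectation and regression to the mean remain.

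The only formal test against non-implanted patients is the safety comparison in 10.6. That is a separate matter, and changing 10.1 and 10.2 does not settle it.

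**Conclusion.** The point holds in limited form. As written, the external comparison in 10.1 cannot show efficacy against no treatment, and the one in 10.2 cannot isolate an effect on tinnitus. The comparison patients have no stated source, entry criteria, treatment status, instruments or adjustment, while the trial subjects are strongly selected. The within-subject results planned in 10.5 are not touched.

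The amount of bias is unknown, and its direction could go either way. The 23.9% and 29.5% at 0.5 SD rest on an assumed imbalance, assumed group sizes and an assumed test. They show that a moderate imbalance would be enough to mislead; they are not properties of this plan. The conclusion itself rests on the text alone and needs none of these numbers. It should be corrected, since the change is small and the affected sentence is in the primary endpoint section.

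**What to change.** - In 10.1, delete the last four words of "has improved safety and efficacy compared to no treatment".
- In 10.1 and 10.2, state that efficacy conclusions rest on the within-subject comparisons: before versus after implantation, and device on versus off where that is tested (speech in noise, sections 2.1 and 8.2). State alongside that the before/after contrast is unmasked and not controlled for time, expectation or regression to the mean.
- If data on non-implanted patients are shown, present them descriptively, with no efficacy claim. Restrict them to patients who meet 4.1 and 4.2 (and have tinnitus, for 10.2), report their device use, and require the same instruments at baseline and one year. Name the data source.

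The cost is an edit to two sections and a more modest efficacy claim. No new visits, measurements or trial subjects are needed. If no outside data meet the restriction, the comparison is simply not shown, and the analysis in 10.5 goes ahead unchanged.

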10.2 Secondary endpoints or outcome measure(s)

The secondary outcome measure of this study is the effect of cochlear implantation on tinnitus suppression in patients with tinnitus in the non-hearing ear. Outcomes will be assessed using the Tinnitus Handicap Inventory and auditory brainstem response testing as previously indicated. Prior studies have indicated that cochlear stimulation via a cochlear implant device can suppress tinnitus. By comparing our findings and measures to data obtained from patients with single sided deafness who do not undergo cochlear implantation, we will better understand the utility of cochlear implantation for tinnitus suppression in this patient population.

10.3 Sample Size Determination

Our study will recruit ten participants for placement of a MAESTRO Cochlear Implant device with follow-up measurements and assessments for one year post-operatively. Although our study is limited to a small sample size of ten patients, the single subject research design will allow each subject to serve as his or her own control, accommodating heterogeneity of the subjects' backgrounds and providing adequate power to test the major hypotheses. Previous studies have used a similar study design and sample size, with statistically significant findings regarding efficacy and safety of cochlear implants in patients with single sided deafness. Given that single-sided deafness is an experimental indication for cochlear implantation, it is appropriate to assess efficacy in a small cohort prior to recruiting more subjects. This will allow us to avoid unnecessary surgery in patients who may not benefit from this intervention.

10.4 Analysis Population

Given the small sample size of ten patients for our study, we will plan to analyze data obtained from all participants. If a subject withdraws from the study, data obtained from their participation in the study will still be incorporated into outcomes and safety analyses.

10.5 Effectiveness Analysis

As this study is a single-subject research design, cochlear implant effectiveness results will be analyzed for each subject individually. The data will be described using conventional descriptive statistics. Data analyses will be conducted using appropriate non-parametric statistical tests. Audiometric and psychoacoustic performance data from the same ear in a subject will be evaluated both prior to and following cochlear implant placement. For all statistical analyses, a $p \le 0.05$ level of significance will be used. Any subsequent deviations from the statistical plan will be described and justified in a protocol amendment and/or in the final report submitted to this application.

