Cochlear implantation in SSD patients has also resulted in significantly improved sound localization and ability to hear in noise (Kamal et al., 2013). One important study examined SSD patients who were treated with cochlear implantation; the untreated side was either normal or treated with a hearing aid. The data demonstrated that, although there was a significant benefit in speech understanding and subjective quality of sound, sound localization only improved in patients with normal hearing on the opposite side (Vermeire and Van de Heyning, 2009). These findings are consistent with a more recent pilot study, in which three patients with short-term SSD and normal hearing in the other ear received a cochlear implant on the deafened side. These patients all achieved open-set speech recognition, improved sound localization, and improved word recognition in noise (Firszt et al., 2012). Another critical study evaluated SSD patients who had undergone cochlear implantation, comparing use of the cochlear implant to a CROS or BAHA. This study found that cochlear implantation resulted in significant gains with respect to objective sound localization and hearing-in-noise testing relative to the CROS or BAHA device in the same patients. Subjective and quality of life measures were also significantly improved with use of the implant (Arndt et al., 2010). Taken together, early data indicate that cochlear implantation in SSD can result in significant tinnitus suppression, improved sound localization and hearing-in-noise, and better quality of life overall.

2 Our hypotheses are that adult patients with postlingual, single-sided deafness who undergo cochlear implantation will 1) wear the implant full-time, 2) report that the cochlear implant provides benefit, 3) show improvement in speech comprehension in quiet and in background noise, 4) demonstrate an improvement in sound localization, and 5) report a reduction in the frequency and intensity of tinnitus compared to before

surgery. To test these hypotheses, we will formally and systematically test patients both before and after surgery as detailed below.

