8.2 Effectiveness Assessments

Effectiveness assessments will be completed based on audiologic testing and subjective questionnaires at each follow-up appointment. These will be compared to the subjects' preoperative baseline measures. In particular, primary dependent measures will include:

- Pure Tone Threshold Audiometry
- Sound Localization Testing (University of Wisconsin Madison)
- Speech Perception Measures Consonant-Nucleus-Consonant (CNC) Testing
- Psychophysical Measures
- Tinnitus Assessment Tinnitus Handicap Inventory (THI)
- Subjective Questionnaires Hearing Handicap Inventory, Abbreviated Profile of Hearing Aid Benefit (APHAB) questionnaire, Speech Spatial and Qualities of Hearing Scale (SSQ), and Quality of Life (SF-36) questionnaire

Each CI subject's speech perception ability will be ranked on a continuum of performance by using standardized speech perception tests that document the range of perception abilities. We will use the Consonant-Nucleus-Consonant (CNC) test (House Ear Institute). The CNC open set single-syllable test will be administered and scored both for whole-word and phonemic items. All speech tests will use recorded materials at a level of 65dB HL and will be presented in the soundfield through a speaker to the subject at 0 degree azimuth and calibrated at a set

distance, typically 1 meter. We will test SSD patients in the bilateral condition, using the good ear only and use contralateral masking to eliminate contributions from the good ear to evaluate the implanted ear.

Each subject's spatial hearing ability will be assessed in collaboration with [name] at the University of Wisconsin. Subjects will identify a single word randomly chosen from a set of fifty possibly alternatives and presented from a loudspeaker directly in front of the subjects. Speech intelligibility will be tested by masking sentences co-presented at different spatial configurations. The presentation level of the target speech will be varied in order to generate different signal-to-noise ratios at each condition. We will evaluate implanted SSD patients with the device turned on and off to directly evaluate contribution of the cochlear implant to understanding speech-in-noise.

Recorded test materials, test keys and patient response forms will be collected and documented as part of the study. Number of test items and percentage scores on each test will be documented and included in the data analysis.

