All subjective questionnaires will serve as an additional qualitative assessment of hearing and will not be used to directly guide quantitative audiologic testing. Measures from subjective questionnaires will be carefully documented for each subject and included in data analysis. These questionnaires will be completed before the activation appointment and prior to each of the follow-up appointments.

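### Section 10.5 analyses effectiveness subject by subject and gives no across-subject test or combining rule for hypotheses about patients as a group; the power claim in 10.3 has no figures behind it

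*Combined protocol and SAP*

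**What the plan says.** Section 10.5 sets the unit of analysis: "As this study is a single-subject research design, cochlear implant effectiveness results will be analyzed for each subject individually". It provides descriptive statistics and then says "Data analyses will be conducted using appropriate non-parametric statistical tests", at a 0.05 significance level for all analyses. No test is named and sidedness is not given. The comparison it describes is within a subject: "Audiometric and psychoacoustic performance data from the same ear in a subject will be evaluated both prior to and following cochlear implant placement".

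Section 3.2 calls the study a single-subject design with up to ten replications. The hypotheses in section 1.2 are worded for patients in general: "Our hypotheses are that adult patients with postlingual, single-sided deafness who undergo cochlear implantation will" use the implant full-time, report benefit, and improve in speech comprehension, localization and tinnitus.

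Section 8.2 widens the before/after comparison beyond audiometry: "Effectiveness assessments will be completed based on audiologic testing and subjective questionnaires at each follow-up appointment". These results are set against the subjects' "preoperative baseline measures. In particular, primary dependent measures will include" six categories, among them the Tinnitus Handicap Inventory (THI) and four further questionnaires.

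Section 10.3 justifies ten participants by saying that each serves as his or her own control, "providing adequate power to test the major hypotheses". It also refers to earlier studies of similar size, without figures.

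**The concern.** A single-subject analysis says whether a given subject changed. The hypotheses ask whether implanted patients as a group change. To get from one to the other, the plan needs either a test across subjects or a stated rule, such as how many of ten subjects must show a significant change. It has neither, so the group conclusion for hypotheses 2 to 5 (benefit, speech, localization, tinnitus) would rest on a method chosen after the data are seen. Hypothesis 1, full-time wear, has no pre-operative value and is outside this point.

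Two consequences follow. Several outcomes are measured once before surgery and only a few times after, so a per-subject significance test on them may be unable to succeed however large the benefit. And readers are told that power is adequate when no calculation stands behind the word.

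**Working it through.** **1. Is there an across-subject effectiveness analysis anywhere?**
- Section 10.5: per subject; test unnamed.
- Section 3.2: replications mentioned; no combining rule.
- Sections 10.1 and 10.2: comparison with single-sided-deafness patients who are not implanted; no effectiveness test named.
- Section 10.6: standard tests for that comparison, but for safety only.

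None fills the gap.

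**2. Can the power claim be reproduced?** No. N = 10 and the 0.05 level are given. The test, sidedness, effect size, SD of change, target power and endpoint are not.

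**3. Smallest attainable p within one subject.** Assume one score per visit. Section 2.2 gives the THI one pre-operative value and three follow-ups (3, 6 and 12 months), and auditory brainstem response (ABR) wave V one pre-operative value and one follow-up (6 months). Section 3.1 gives the hearing-handicap and SF-36 questionnaires at most four post-operative values.

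Formulas:
- Rank-sum, 1 baseline versus m follow-ups: one-sided minimum 1/(m+1), doubled for two-sided.
- Sign or signed-rank on m differences from baseline: one-sided minimum 0.5^m, doubled for two-sided.

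| Follow-ups | Rank-sum, one-/two-sided | Sign or signed-rank, one-/two-sided |
|---|---|---|
| 1 | 0.50 / 1.0 | 0.50 / 1.0 |
| 3 | 0.25 / 0.50 | 0.125 / 0.25 |
| 4 | 0.20 / 0.40 | 0.0625 / 0.125 |

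Section 8.2 also says: "These questionnaires will be completed before the activation appointment and prior to each of the follow-up appointments". Treating the score taken before activation as a second baseline gives 2 versus 3 values: 1/C(5,2) = 0.10 one-sided, 0.20 two-sided. No entry reaches 0.05. A five-point monotone trend test could (2/5! = 0.0167 two-sided), but it asks about a steady trend over visits, not a before/after change.

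**4. Outcomes with many items or trials.** CNC words and localization trials can be tested within a subject, so the floor in step 3 does not apply. Ten such tests then need a rule. With no true effect, independent tests and exact size 0.05, the number of significant subjects is binomial(10, 0.05):
- at least one: 1 − 0.95^10 = 40.1%
- at least two: 8.6%
- at least three: 1.2%

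The false-positive rate therefore depends wholly on a rule that the plan does not state.

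**5. What an across-subject test would deliver.** Exact Wilcoxon signed-rank, two-sided 0.05, normally distributed changes, power by simulation. The standardized mean changes are assumptions, because the documents give none.

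| Pairs | Attained size | 0.5 SD | 0.8 SD | 1.0 SD | Change for 80% power |
|---|---|---|---|---|---|
| 8 | 0.0391 | 19% | 43% | 61% | about 1.26 SD |
| 10 | 0.0488 | 28% | 60% | 78% | about 1.02 SD |

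**The case against.** The strongest reply is that single-subject designs with replication are legitimate and that section 3.2 declares one. Generalisation then comes from replication, and step 4 shows that a count rule, such as three or more significant subjects of ten, would have a low false-positive rate for CNC and localization. That stands, and it narrows the gap to a missing test or combining rule. It does not remove it: no rule is stated, and a count rule cannot serve outcomes for which no single subject can reach significance.

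Second, section 10.5 does not prescribe a per-subject significance test on questionnaires. Its before/after sentence names audiometric and psychoacoustic data, section 8.2 calls the questionnaires an additional qualitative assessment, and descriptive statistics are provided for. This also stands. A reader might infer from step 3 that the plan's tinnitus and questionnaire results can never be significant. The documents do not support that: the floor holds only for one score per visit and only if the per-subject rule is applied to those scores. Nor does the unnamed non-parametric test exclude an across-subject one; the plan simply does not specify it.

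Third, section 10.3 presents ten patients as a first cohort before wider recruitment, and section 1.2 cites 80–95% of patients improving in tinnitus. Under the normal-change model those shares correspond to about 0.84 to 1.64 SD (the standard normal quantiles), where signed-rank power is 64% to 99% with ten pairs and 47% to 96% with eight. So a reader should not conclude that ten is too few. That figure concerns tinnitus in a cited series, however, and section 10.3 does not use it.

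A reader might also take the 40% in step 4 as the trial's error rate. It is not, because no section declares success on one significant subject.

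**Conclusion.** The point holds, and the plan should be amended. No section gives an across-subject effectiveness test or a rule for combining the single-subject results, so nothing pre-specified answers hypotheses 2 to 5 for the group. The planned comparison with non-implanted patients does not repair this. For outcomes with one score per visit, a before/after rank-sum, sign or signed-rank test within a subject cannot reach 0.05; this is conditional on that scoring and on the per-subject rule being applied to them. The power claim in 10.3 is unsupported rather than shown to be false: ten pairs are adequate by the usual 80% standard if the true mean change is about 1 SD or more, and not if it is clearly smaller. These power figures assume normally distributed changes.

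**What to change.** **Section 10.5**
- Add an across-subject exact Wilcoxon signed-rank test of the change from pre-operative to 12 months (6 months for ABR; the Madison visit after 12 months for localization). Report the Hodges-Lehmann median change with 95% CI.
- Include all implanted subjects with both values. Report the number missing, and show the data of withdrawn subjects without a final value descriptively, in keeping with section 10.4.
- For speech-in-noise, keep the device-on versus device-off contrast of sections 2.1 and 8.2, tested across subjects with the same paired test. Report pre-operative acoustic ear versus post-operative bilateral as supportive.
- Show per-subject results descriptively, with per-subject tests only for item- or trial-level data.
- Name one primary outcome from the section 8.2 list before any outcome data are analysed, including at the interim looks of section 10.7. Test it once, at the final analysis, at two-sided 0.05. Keep effectiveness at the interim looks descriptive, and label all other p-values unadjusted and exploratory.

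**Section 10.3**
- Replace the power claim with the detectable change and its assumptions: about 1.02 SD for 80% power with ten pairs and about 1.26 SD with eight, with power of 28%, 60% and 78% at 0.5, 0.8 and 1.0 SD for ten pairs.

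**Cost.** Wording only; no extra patients, visits or data. The sponsor-investigator must commit to one primary outcome, the others become exploratory, and the power statement becomes less favourable.
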